9.8.5 Trial product destruction

Please refer to the trial product handling manual regarding details for trial product destruction.

9.9 Provision for subject care following trial completion

In order to ensure appropriate treatment of the subjects after they have completed the trial, the subjects will be treated at the investigator's discretion or referred to other physician(s) according to standard practice. Subjects who qualify for the long-term extension trial (see Section 7.1) may be offered participation (selected countries).

9.10 Reporting product complaints

Any defects or issues with the IMP, AxMP (TCS) as well as any IMP device deficiency (including malfunctions, use errors, and inadequate labelling) must be reported to Global Safety at LEO on the trial-specific (paper) Complaint Form within 3 days of first knowledge.

Critical complaints (defined as any defect, issue, or device deficiency that has or potentially could have a serious impact for the subject [e.g., SAE or large particles in the syringe]) must be reported to Global Safety, LEO within 24 hours.

Complaint forms should contain a detailed description of the defect, issue, or device deficiency, including whether it led to an AE. (S)AEs which occur due to a defect or issue with the IMP or due to a device deficiency will be reported by the investigator as described in

Sections 13.3 and 13.4. Similarly, any defects or issues with TCS must be reported to Global Safety using the same complaint procedure as for the IMP and device.

Refer to the IRT training manual for information on how to update the kit status in the IRT.

During the investigation of the product complaint, the IMP or device must be stored at labelled conditions unless otherwise instructed; the trial site will be notified whether the IMP or device needs to be returned for further investigation or may be destroyed.

Global Safety, LEO contact information for reporting product complaints:

[contact]

E-mail address: [contact]

10 Discontinuation and withdrawal

10.1 General principles

A subject may permanently discontinue trial treatment (IMP) or withdraw from the trial at any time (prior to first dose or during the treatment period) if the subject, the investigator, or LEO considers that it is not in the subject's best interest to continue.

In order to obtain the most representative efficacy evaluation of tralokinumab, it is key to assess the efficacy status of each trial participant at the planned primary and secondary endpoints (nominal Week 16 and 26 visits), irrespective of whether the subject has discontinued IMP or not (see [Panel 2](#)). Hence, permanent discontinuation of IMP and withdrawal from trial are considered to be (potentially) 2 separate occurrences:

- **Permanent discontinuation of IMP** occurs when all further trial treatment is stopped. The subject will continue to participate in selected trial visit activities as outlined in [Section 10.3](#) (see [Panel 6](#) for additional visits required following permanent discontinuation of IMP).
- **Withdrawal from trial** occurs when stop of all trial activities takes place before the last planned safety follow-up visit (Week 40). This may either happen at the time of permanent discontinuation of IMP or later.

Subjects who permanently discontinue IMP and subjects who withdraw from the trial will not be replaced.

10.2 IMP discontinuation rules

10.2.1 Reasons for permanent discontinuation of IMP

Subjects will permanently discontinue IMP in the event of:

- Anaphylactic reaction or other severe systemic reaction to IMP injection.
- An AE that, in the opinion of the investigator or sponsor's medical expert, contraindicates further dosing.
- Diagnosis of a malignancy during the trial, excluding carcinoma in situ of the cervix, or localised squamous or basal cell carcinoma of the skin.
- Evidence of pregnancy.
- Any infection that is opportunistic, such as active tuberculosis and other infections whose nature or course may suggest an immuno-compromised status.

- Severe laboratory abnormalities:
 - ALT and/or AST values $>3\times\text{ULN}$ with total bilirubin $>2\times\text{ULN}$ (unless elevated bilirubin is related to Gilbert Meulengracht Syndrome).
 - Confirmed AST and/or ALT $>5\times\text{ULN}$ (for more than 2 weeks).

10.2.2 Reasons for temporary discontinuation of IMP

IMP dosing may be temporarily suspended in the event of:

- Other intercurrent illnesses or major surgery.
- An infection that requires parenteral treatment with antibiotic, antifungal, antiviral, anti-parasitic, or anti-protozoal agents.
- Treatment with systemic corticosteroids or non-steroidal immunosuppressive/immunomodulating medications (e.g., methotrexate, azathioprine, mycophenolate mofetil, Janus kinase inhibitors, biologic agents). After the treatment with these medications is completed, IMP may be resumed if deemed appropriate by the investigator, but not sooner than 5 half-lives after the last dose of systemic therapy.

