9.5 Rescue treatment

If medically necessary (i.e., to control intolerable AD symptoms), rescue treatment for AD may be provided to trial subjects at the discretion of the investigator. If possible, investigators should attempt to limit the first step of rescue therapy to topical medications (i.e. higher potency TCS, Europe class >3), and escalate to systemic medications only for subjects who do not respond adequately after at least 14 days of topical treatment. The subject will be monitored for signs of local or systemic TCS toxicity and the safety and appropriateness of continued use will be supervised by site staff.

Subjects who receive topical rescue treatment (higher potency TCS, Europe class >3) will continue IMP treatment.

If a subject receives rescue treatment with systemic corticosteroids or non-steroidal systemic immunosuppressive drugs (methotrexate, mycophenolate mofetil, azathioprine, etc.), IMP will be immediately discontinued (see Section 10.2.2). After the treatment with these medications is completed, IMP may be resumed if deemed appropriate by the investigator, but not sooner than 5 half-lives after the last dose of systemic rescue treatment. The use of biological rescue treatment will be disallowed for the entire trial duration.

Investigators should make every attempt to conduct efficacy and safety assessments (at least disease severity scores [IGA and EASI], concomitant medications/ procedures, and AEs) immediately before administering any rescue treatment. An unscheduled visit may be used for this purpose, if necessary. In the primary efficacy analyses, subjects who receive higher potency TCS (Europe Class >3) or systemic rescue treatment during the treatment period will be considered as non-responders.

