9.7 Prohibited medication and procedures

The medications listed below are prohibited during the trial from randomisation. Medications and procedures disallowed prior to randomisation are covered in the exclusion criteria (see Section 8.3). In case any prohibited treatments are used during the trial, they must be recorded as concomitant medication.

From randomisation through end of treatment (Week 26):

- PDE-4 inhibitors.
- TCS of higher potency (Europe class >3).
- Use of UVA or UVB, psoralen + UVA (PUVA), other phototherapy, or tanning beds.
- 3 or more bleach baths per week.

From randomisation through safety follow-up (Week 40):

- Investigational agents other than tralokinumab.

- Systemic corticosteroids (nasal and inhaled corticosteroids are allowed).
- Systemic treatment for AD with an immunosuppressive/immunomodulating agent (examples include: cyclosporine A, mycophenolate mofetil, azathioprine, methotrexate, Janus kinase inhibitors, interferon-gamma, dupilumab, or other biologics).

In case prohibited systemic medications are received (for any indication), IMP dosing must be suspended as described in Section 10.2.2.

The sponsor's medical expert must be notified if a subject receives any of the following prohibited medications from randomisation through safety-follow-up (Week 40):

- Allergen immunotherapy.
- Live (attenuated) vaccine.
- Immunoglobulins.
- Blood products.

The sponsor's medical expert will determine whether IMP discontinuation is required. Please note that receipt of inactive/killed vaccines (e.g. inactive influenza) is allowed, provided they are not administered within 5 days before/after any trial visit.

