3. From the date of permanent discontinuation of IMP due to the COVID-19 pandemic.

The date of this event will be the date of the administration of rescue treatment.

- **Prolonged interruption of IMP dosing due to the COVID-19 pandemic:**

A temporary pause in dosing due to the COVID-19 pandemic may influence the interpretation of the subsequent outcome for the subject, and the event will therefore be reported.

At the first occurrence, for which a subject misses IMP doses in one of the 4 following scenarios, the subject will be defined as having a prolonged interruption of IMP due to the COVID-19 pandemic:

1. 3 consecutive missed IMP doses, for which at least one of them is due to the COVID-19 pandemic.
2. 2 consecutive missed IMP doses, for which at least one of them is due to the COVID-19 pandemic and the third consecutive IMP dose is delayed for more than 7 days beyond the planned date of the IMP dosing.
3. Week 22 and Week 24 IMP doses and the Week 26 visit are missed, for which at least one of them is due to the COVID-19 pandemic.
4. Week 22 and Week 24 IMP doses are missed, for which at least one of them is due to the COVID-19 pandemic, and the Week 26 visit is delayed for more than 7 days beyond the planned date.

In scenarios 1 and 3, the start date of the event will be the planned date of the third consecutive missed IMP dose or the Week 26 visit. In scenarios 2 and 4, the start date of the event will be the planned date of the third consecutive IMP dose +7 days or the Week 26 visit + 7 days.

- **Missing data due to the COVID-19 pandemic:**

The collection of data at planned visits allows to report if data is missing due to the COVID-19 pandemic, either due to the subject being prohibited from visiting the sites or the visit being performed via telephone/video, thereby only allowing for a subset of data to be collected.

In the context of some of the efficacy analyses, data recorded missing due to the COVID-19 pandemic will be handled differently from data missing for other reasons. As an example, it may not be reasonable to impute missing binary responder values as a non-response if the missingness is due to the COVID-19 pandemic.

It should be noted that a subject may have missing data due to the COVID-19 pandemic, even though the subject may not have discontinued IMP permanently or temporarily due

to the COVID-19 pandemic. This could e.g. be the case if the subject continue treatment with tralokinumab via home-use ([Appendix 8](#)).

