14.3.4 Exposure and treatment compliance

Exposure

Exposure to treatment will be presented for the safety analysis set as days of exposure per treatment group.

Treatment compliance

Compliance to treatment regimen will be recorded in the eCRF. If any complications or deviations in administration are observed, these will be described as protocol deviations. Treatment compliance will be presented for the total missed IMP doses, missed IMP doses not due to the COVID-19 pandemic, and the missed IMP doses due to the COVID-19 pandemic for the safety analysis set for each treatment group.

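### Protocol 10.2.2 makes it optional to suspend IMP during systemic corticosteroids or immunosuppressants; 9.5 and 9.7 make it compulsory and cite 10.2.2 for the rule.

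*Protocol*

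**What the plan says.** Three sections of the current protocol text govern what happens to IMP when a subject receives systemic corticosteroids or immunosuppressive or immunomodulating drugs.

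- Section 10.2.2, on temporary discontinuation, opens its list with "IMP dosing may be temporarily suspended in the event of". The list has three items: other illness or major surgery, infections treated parenterally, and treatment with the systemic drugs above. The third item adds that "IMP may be resumed if deemed appropriate by the investigator, but not sooner than 5 half-lives after the last dose of systemic therapy".
- Section 9.5, on rescue treatment for AD, says that with systemic corticosteroid or immunosuppressant rescue "IMP will be immediately discontinued (see Section 10.2.2").
- Section 9.7, on prohibited medication, says: "In case prohibited systemic medications are received (for any indication), IMP dosing must be suspended as described in Section 10.2.2". Its list of what is prohibited includes "Systemic corticosteroids (nasal and inhaled corticosteroids are allowed") and, as a separate item, "Systemic treatment for AD with an immunosuppressive/immunomodulating agent".

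No clause in the protocol says which section prevails, and the SAP does not address the matter.

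**The concern.** Section 10.2.2 sits under the discontinuation rules and is the target of both cross-references, so it is where an investigator would look. The text found there grants discretion over a step that the two citing sections treat as compulsory. An investigator who reads only 10.2.2 could reasonably continue the investigational biologic while the subject is on systemic immunosuppression. Another who starts from 9.7 would stop. With about 40 sites planned (7.2), subjects in the same situation could be dosed differently, and some would be dosed when the protocol says they must not be.

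**Working it through.** There is no figure to reproduce and no arithmetic applies. The check is a comparison of texts.

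**Step 1. The three rules side by side.**

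| Section | Trigger | Force | Cites 10.2.2? |
|---|---|---|---|
| 9.5 | Systemic rescue for AD | Compulsory ('will') | Yes |
| 9.7 | Prohibited systemic medications | Compulsory ('must') | Yes |
| 10.2.2 | Systemic corticosteroids or immunosuppressants, with no AD limit | Optional ('may') | – |

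**Step 2. What 'may' means in 10.2.2.** The neighbouring 10.2.1, on permanent discontinuation, introduces its list with 'will'. Within the same 10.2.2 item, the resumption sentence uses 'may' for investigator discretion ("IMP may be resumed if deemed appropriate by the investigator, but not sooner than 5 half-lives after the last dose of systemic therapy"). Discretion also suits the other two items. The natural reading is therefore permissive, and one compulsory item has been placed under a discretionary opening. The minimum interval before resumption makes sense only if dosing has stopped, so the intent appears to match 9.5 and 9.7.

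**Step 3. Which conduct complies.**

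| Conduct | 10.2.2 | 9.5 (AD rescue) | 9.7 |
|---|---|---|---|
| Suspend IMP | Complies | Complies | Complies |
| Continue IMP | Complies as written | Breach | Breach |

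**Step 4. How far the conflict reaches.**

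- AD rescue with these drugs: clear, from 9.5 and 9.7.
- Systemic corticosteroids for any reason: clear, because the 9.7 item carries no AD limit.
- Immunosuppressants for another disease: less explicit. The 9.7 item is worded as "Systemic treatment for AD with an immunosuppressive/immunomodulating agent", so a compulsory stop depends on reading the bracketed words about indication in "In case prohibited systemic medications are received (for any indication), IMP dosing must be suspended as described in Section 10.2.2" as widening that item.

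**Step 5. What reaches the primary analysis.**

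- AD rescue that meets the 14.3.5 definition is non-response under 14.3.8.1 whether or not IMP continued. If subject-onset of COVID-19 came first, the value is imputed under MAR, again whether or not IMP continued.
- Use for another disease is not rescue under 14.3.5, and a temporary hold is not one of the three intercurrent events in 14.3.7. The observed Week 16 value is normally used in either case.
- Nothing here enters the sample size statement in 14.1 or the testing hierarchy in 14.3.6.

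**The case against.** The strongest reply is that the sections can be reconciled. Section 10.2.2 lists reasons that allow a temporary rather than a permanent stop, 9.5 and 9.7 carry the obligation, and they cite 10.2.2 only for the mechanics. A similar pattern appears for intercurrent illness, where 10.2.2 says 'may' and 9.2.1 says that IMP should not be given until a rescheduled visit. This reading is possible but strained, for the reasons in step 2. The illness comparison is also weaker than it looks: 9.2.1 makes that hold depend on the investigator's opinion, so 'may' fits there. For systemic drugs 9.7 leaves no such judgement.

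Part of the reply stands. A permission in one section does not cancel a prohibition in another. Section 14.3.4 says "If any complications or deviations in administration are observed, these will be described as protocol deviations", and a reader might infer that whether continued dosing counts as a deviation depends on which section is applied. It does not: dosing through breaches 9.7 whatever 10.2.2 says.

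A reader might also infer a route into the primary analysis through the COVID-19 rules. Section 14.3.1 treats as a prolonged interruption "3 consecutive missed IMP doses, for which at least one of them is due to the COVID-19 pandemic", so two held doses followed by one COVID-19 miss would be 2 + 1 = 3 and could lead to imputation at Week 16. This assumes that held doses count as missed, and it runs the wrong way. The compulsory hold produces the three misses, while dosing through leaves 0 + 1 = 1 miss and the observed value. It is not a harm caused by 'may'.

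Finally, the documents give no safety reason for the hold, and the protective measures in 5.6 do not mention it. The subject-protection argument therefore rests on the protocol's own decision to make the stop compulsory, not on a stated risk.

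**Conclusion.** Section 10.2.2 is wrong as written and should be corrected. An operative dosing instruction grants discretion that the two sections citing it withhold. The contradiction is certain for AD rescue and for systemic corticosteroids given for any reason; for non-AD immunosuppressants it depends on how 9.7 is read.

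The consequence is for subject protection and consistent dosing. There is no effect on alpha, power or sample size, and no material effect on the primary analysis is shown. The size of the practical problem cannot be given, because the documents state neither how many subjects might receive these drugs nor how long courses would last. The conclusion assumes only that 'may' has its ordinary permissive meaning.

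**What to change.** Split the list in 10.2.2:

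1. IMP dosing must be suspended during treatment with systemic corticosteroids or immunosuppressive or immunomodulating drugs, with the five-half-life resumption sentence unchanged.
2. IMP dosing may be temporarily suspended for other illness or major surgery, and for infections treated parenterally.

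The sponsor should confirm whether the any-indication wording in 9.7 covers immunosuppressants given for diseases other than AD, word item 1 to match, and notify sites. Section 9.5 needs no change.

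The cost is a short amendment, with authority and ethics committee approval as required before implementation (Appendix 3A), and a site letter. The SAP, data collection and sample size are untouched.

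The documents do not say whether dosing was still under way when the SAP was dated (21-Oct-2020). If it is complete, an amendment serves no purpose. The sponsor should then apply 9.7 when it assesses protocol deviations for the clinical trial report (Appendix 3D, protocol compliance).

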10.3 Early termination assessments

Permanent discontinuation of IMP

Subjects who permanently discontinue IMP for any reason will be asked to attend additional visits as indicated below ([Panel 6](#)). See the schedule of trial procedures for data to be collected at these visits ([Section 4](#)). The investigator will review any AEs which will be followed up according to [Section 13.7](#), if the subject agrees.

Panel 6: Additional visits after permanent discontinuation of IMP

IMP discontinuation stage	Additional visits required
Prior to Week 16	
 • Early termination visit • Nominal Week 16 visit (16 weeks after randomisation) • Nominal Week 26 visit (26 weeks after randomisation) • Final SFU visit (16 weeks after last administration of IMP)
After Week 16 and prior to Week 26	
 • Early termination visit • Nominal Week 26 visit (26 weeks after randomisation) • Final SFU visit (16 weeks after last administration of IMP)
After Week 26 and prior to Week 40	
 • Early termination visit • Final SFU visit (16 weeks after last administration of IMP)

Abbreviations: IMP, investigational medicinal product; SFU, safety follow-up.

Withdrawal from trial

A subject may withdraw from the trial at any time and for any reason. Subjects who withdraw from the trial should attend an early termination visit (if applicable), see the schedule of trial procedures (Section 4) for data to be collected at an early termination visit. The investigator will review any AEs which will be followed up according to Section 13.7, if the subject agrees. If a subject withdraws from the trial, they may request destruction of any samples taken and not tested, and the investigator must document this in the site's trial records.

Data to be recorded in the eCRF and medical records

The reason for permanent discontinuation of IMP must be recorded in the medical records and in the eCRF (on the end-of-treatment form and end-of-trial form). The reason for subject withdrawal must be recorded in the medical records and in the eCRF (end-of-trial form). For subjects who do not attend the nominal visits at Week 16 or Week 26 or the safety follow-up visit, the reason for not attending will be recorded in the medical records and in the eCRF.

The categories for assigning reasons in the eCRF are: 'lack of efficacy', 'AE', 'withdrawal by subject', 'lost to follow-up', 'death', or 'other'. If 'AE' or 'other' is selected, a specification must be provided in the eCRF.

10.4 Lost to follow-up

A subject will be considered lost to follow-up if they repeatedly fail to return for scheduled visits and if the trial site is not able to get in contact with the subject.

The following actions must be taken if a subject fails to return to the trial site for a required visit:

- The trial site must attempt to contact the subject and reschedule the missed visit as soon as possible and counsel the subject on the importance of maintaining the assigned visit schedule and ascertain whether or not the subject wishes to continue in the trial.
- Before a subject is deemed lost to follow-up, the investigator or designee must make every effort to regain contact with the subject (where possible, 3 telephone calls and, if necessary, a certified letter to the subject's last known mailing address or local equivalent methods). These contact attempts should be documented in the subject's medical record. Should the subject continue to be unreachable, they will be considered to have withdrawn from the trial with a primary reason of lost to follow-up.

11 Trial assessments and procedures

11.1 Overview

During the trial there are 17 scheduled site visits at the clinic. Evaluations to be done at each visit are shown in the schedule of trial procedures in Section 4:

- [Panel 2](#) includes the assessments during screening and treatment.
- [Panel 3](#) includes the assessments during follow-up (including early termination and unscheduled visits).

Refer to Section 7.1 for further details on the trial design.

Assessments/procedures at any trial visit should be performed in the order assigned below:

- PROs:
 - DLQI
 - EQ-5D-5L
 - POEM
 - HADS
 - SF-36
- Investigator assessments/procedures:
 - SCORAD component C, then component A and B
 - IGA
 - EASI
- Safety and laboratory assessments (including PK)
- Other assessments (photographs)
- Administration of IMP

Subjects may also need to be seen at unscheduled visits during the course of the trial. The assessments performed at an unscheduled visit are left at the investigator's discretion, except if the unscheduled visit involves administration of rescue treatment. In that case, the investigator should make every attempt to conduct efficacy and safety assessments (at least disease severity scores [IGA and EASI], concomitant medications/procedures, and AEs) immediately before administering any rescue treatment. An unscheduled visit may include any assessment performed at an early termination visit, see [Panel 3](#) for details.

Subjects participating in the trial will be under careful supervision of a qualified principal investigator (see [Appendix 1.4](#)). Investigators must be experienced in treating AD and have documented experience and/or training in use of the assessments required by the protocol and must be either a physician, certified physician's assistant, or advanced registered nurse practitioner.

AEs must be assessed by medically qualified personnel (Section [13.2](#)).

To reduce inter-rater variability, the same investigator should preferably perform all the efficacy evaluations (IGA, EASI, SCORAD) for a given subject throughout the entire trial period.

The investigators performing the assessments must not be involved in the administration of IMP (Section [9.3.1](#)).

